	

ii. Wound infection (y/n)

c. Length of stay (days; typically 0 to 1)

i. Discharge date/time (m-d-y; hh:mm)

3. Use of postoperative pain medication

a. Opioids (y/n for each: fentanyl, Dilaudid, oxycodone, Norco, tramadol, Percocet, Demerol)

i. Morphine equivalents (MME)

b. Non-opioids (y/n for each: Toradol, Tylenol, oxybutynin)

4. Postoperative pain scores (0-10; asleep, missed, or discharged)

a. Average and maximum scores during each interval (during the PACU stay, the first 4 hours on the floor, next 8 hours, and the following 8 hours; as well as the final score immediately prior to discharge)

b. At each location (abdomen, legs, groin, scrotum, shoulder, other/specify)

5. Timing of ability to pass gas (day 0, day 1, day 2, >day 2)

6. Clinically-significant ileus (i.e., requiring treatment; y/n)

Follow-Up (1 week, 1 month, & 3 months)	

1. QoR-15 (0-150) – only asked at week 1

a. Collected (y/n)

b. Score (0-150)

2. Prescription(s) given (y/n) – only asked at week 1

a. Prescription(s) filled (y/n)

b. Opioids (y/n for each: fentanyl, Dilaudid, oxycodone, Norco, tramadol, Percocet)

i. Number of pills taken for each (#)

ii. Morphine equivalents (MME)

c. Non-opioids (y/n for each: Toradol, Tylenol, oxybutynin)

3. Scrotal swelling (y/n) – only asked at week 1

4. Leg weakness (y/n)

a. Left, right, bilateral

b. Degree of weakness (each leg; mild, moderate, severe)

c. Impaired ability to walk

d. Impaired ability to drive

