We will collect information on pertinent surgical outcomes that occur through discharge. The average amount of time spent in the PACU is roughly 1-2 hours, and the average hospital length of stay is 0-1 days. For Intraoperative Item #2, a deviation from the standard port number/size(s)/locations would be due to body habitus, and will not have an effect on clinical outcomes. For Intraoperative Item #3, continuous values will be exported into individual patient-specific Excel spreadsheets with the assistance of the CareConnect Systems Analysts. This is due to the fact that there are far too many data points (8 different variables every 1 minute for 120 minutes) to be manually extracted and subsequently manually entered. The PI will perform individual analyses on these data sets in conjunction with Analysts, and

calculate means and standard deviations to be entered into REDCap. For Intraoperative Item #15, we are collecting whether the obturator artery was affected for each leg, as this could potentially be a confounder to postoperative leg pain (i.e., increased pain in the affected leg). Finally, the presence of wound infection (in the PACU and on the Floor; Postoperative Items #1b-iii and #2b-iii, respectively), as well as clinically-significant ileus (on the Floor; Postoperative Item #6) will be evaluated and assessed by nursing staff per routine care and entered into the medical record.

The Quality of Recovery (QoR)-15 questionnaire (Appendix E) is used to evaluate recovery from anesthesia. The tool consists of 15 questions that assess patient-reported quality of postoperative recovery using an 11-point (i.e., 0-10) numerical rating scale, where "0" refers to "all of the time [poor]" and "10" refers to "none of the time [excellent]." Therefore, a higher score refers to better quality of recovery. The questionnaire assesses basic and essential activities of daily life (ADLs), pain, emotions, and personal/overall well-being, among others. The survey will be administered at the 1-week follow-up visit only, and takes approximately 2-3 minutes to complete.

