will be educated on the importance of bringing all medications to follow-up visits, which will lead to more accurate pain medication counts and calculations.

Patients are typically discharged on Day 0-1, and for those discharged on Day 0 (i.e., same-day), the CRC will call the following morning to evaluate pain (see Appendix C). Because we are targeting same-day or next-day discharge, there is the potential for missing data in the first 24-hour period. Therefore, there will be no restrictions or protocol deviations for pain scores, as we are collecting scores only while inpatient/awake and via phone call for those discharged same-day. Follow-up visits per routine care occur at approximately 1 week postoperatively for catheter removal, as well as at 1 month and 3 months. Appointments will follow routine scheduling practices for the office, which may include variance in exact visit timing. Generally, patients will have 1 week postoperative visit around 5-7 days after surgery, but may be delayed further by approximately 1 week depending on scheduling availability and/or clinical indication (e.g. need for cystogram). Follow-up visits are generally 1 month and 3 months post-surgery, but may occur approximately a couple weeks before or after as per physician standard of care scheduling to accommodate patient and physician availability. There will be no strict visit windows to allow for visit scheduling flexibility. Because the majority of RALP patients will be eligible for participation, schedulers will be educated on the importance of return visit timing accuracy. There will be no extended or long-term follow-up via direct patient contact or EMR review.

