Patients that are unable to pass gas while inpatient will be called on postoperative day 1 (if discharged same-day only) and day 2. The post-operative day 1 phone call will also be utilized to assess pain for those who were discharged same-day, as explained above. If a patient confirms that they have passed gas on day 1, they will not be called again on day 2. For Thursday/Friday procedures where days 1 and/or 2 (as applicable) fall on the weekend, patients will be called on Monday morning and asked to recall when they were able to pass gas (i.e., whether it occurred on Saturday or Sunday). If patients are not discharged same-day, they will only receive a single phone call on day 2 if they did not pass gas prior to discharge. Patients who are not discharged same-day and are able to pass gas prior to discharge will not receive any phone calls. In the case that a patient is still unable to pass gas on day 2, we will repeat phone calls daily until they are able to do so, although we do not anticipate many patients will need to be called past day 2. We are collecting this data due to recent anecdotal evidence in Robotic Urology that patients who receive Percocet were able to pass gas on average in 1.6 days versus 1.4 days for those that did not receive Percocet.

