**Table 3. Study Calendar.**

	Baseline	Surgery & Post-Op Stay	Days 1 & 2 (post-discharge)	1-Week Follow-up	1-Month Follow-up	3-Month Follow-up
Informed Consent	x					
Randomization		x				
Office Visit	x			x	x	x
Intra- & Post-Op DCF		x				

(Appendices A&B)						
Post-Discharge DCF (Appendix C)			x*			
Follow-Up DCF (Appendix D)				x	x	x
QoR-15 (Appendix E)				x		
Phone Calls			x			

\* Patients will be called for pain scores on day 1 if discharged same day; patients will be called on days 1 & 2 to assess the ability to pass gas.

We do not expect any treatment-related adverse events (AEs) or excess risk associated with randomization to the study group, as all surgical procedures are considered routine care. Therefore, we will not be tracking treatment-related AEs, only treatment-related serious adverse events (SAEs), which will be reported to the OhioHealth IRB via IRBNet reporting using the Adverse Event Template Form, per institutional and national guidelines, within 10 business days of discovery or notification of the event. SAEs will be tracked for 90 days following discharge via chart review. Patients will be removed from the study only if they revoke their informed consent prior to surgery. There are no intraoperative events that would warrant study removal, and changes in insufflation pressure will be recorded intraoperatively as mentioned above. Further, patients who do not return for follow-up visits (which is not anticipated in this population) will still be analyzed in the final dataset.

Only de-identified or non-identifiable data will be reported in the study. Only the IRB-approved study staff will have access to patient information. All resulting data will be stored in electronic format; electronic files will be stored on a password-protected computer and paper files will be stored in a secure facility with limited access (the offices of the OhioHealth Research Institute). Participants will not be excluded on sexual orientation, socioeconomic, racial, or religious identity. The data collection and storage processes will follow HIPAA guidelines in accordance with 21 CFR 46.115 (b): to protect both confidentiality and privacy of each participant. All PHI data will be released or destroyed per institution protocol.

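### Aim 4 could report a shorter stay at 6 mmHg without an all-cause count, by arm, of patients who came back after discharge

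*Combined protocol and SAP*

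**What the plan says.** **Adverse events (section 2.3, after Table 3).** The plan expects no excess risk from allocation to 6 mmHg and continues: "Therefore, we will not be tracking treatment-related AEs, only treatment-related serious adverse events (SAEs". On duration it says: "SAEs will be tracked for 90 days following discharge via chart review". That sentence does not repeat the relatedness limit. The text shown defines neither serious nor treatment-related.

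**In-hospital outcomes (section 2.2, after Table 1).** "We will collect information on pertinent surgical outcomes that occur through discharge". The items include "the presence of wound infection (in the PACU and on the Floor; Postoperative Items #1b-iii and #2b-iii, respectively"), and "clinically-significant ileus (on the Floor; Postoperative Item #6) will be evaluated and assessed by nursing staff per routine care". The same section puts the average stay at 0-1 days.

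**After discharge.**
- The Table 1 follow-up block covers 1 week, 1 month and 3 months and has four items: QoR-15, prescriptions with pills taken, scrotal swelling and leg weakness. The first three are marked "only asked at week 1".
- Section 2.3 adds a next-morning pain call for patients discharged on the day of surgery.
- It also adds calls about passing gas. If gas has not passed by day 2, "we will repeat phone calls daily until they are able to do so".

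**Length of stay.** Section 1.1 hypothesises that low pressure might allow a shorter stay. Aim 4 in section 2.4 compares mean stay and the day-0 versus day-1 split, and treats a 10-point difference as clinically significant.

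**The concern.** Earlier discharge is a benefit only if patients do not then return more often. As listed, the data would show that a patient went home on day 0. They would not show that he came to an emergency department on day 4, unless the event was classed as a treatment-related SAE. A non-serious return, or one judged unrelated, has no listed field. Aim 4 could then favour one arm with no all-cause figure beside it. This matters because the end of section 2.3 intends the results to encourage lower pressure across laparoscopic and robotic surgery.

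A second, smaller issue is that recording of wound infection and ileus stops at discharge. If 6 mmHg does shorten stay, that arm is observed for less time, and its recorded count falls for reasons unrelated to risk.

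**Working it through.** **1. Inputs.** Section 2.4 gives 86 per group, and section 2.1 gives 96 per group enrolled. The plan's sample size reproduces. With a difference of 0.7 and SD 1.4 (effect size 0.5), two-sided 0.05 and 90% power, the t-test calculation gives 85.03, rounded up to 86. Then 172/0.9 = 191.1, rounded up to 192. The plan gives no complication, return or same-day discharge rate, so every rate below is an assumption.

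**2. What is listed after discharge.** Of four follow-up items in Table 1, three are for week 1 only. That leaves 4 − 3 = 1 item, leg weakness, at 1 and 3 months. None of the four is a readmission, emergency visit or reoperation. SAEs are not in Table 1, and section 2.4 names no SAE comparison.

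**3. Scale of the uncounted outcome.** If 5% to 20% of patients returned for any reason, that would be 0.05 × 96 = 4.8 to 0.20 × 96 = 19.2 patients per arm. How many would be classed as treatment-related SAEs cannot be read from the documents. The unlisted share could lie anywhere between none and all.

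**4. Size of the window bias.** Let p be the true risk, equal in both arms, and s the same-day discharge share. Let f0 and f1 be the fractions of events seen in hospital after day-0 and day-1 discharge. Expected recorded events per arm = n·p·[s·f0 + (1 − s)·f1]. With n = 96 and p = 0.05:

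| f0, f1 | s (15 vs 6 mmHg) | Recorded, 15 mmHg | Recorded, 6 mmHg | Ratio (6 / 15 mmHg) |
|---|---|---|---|---|
| 0.10, 0.40 | 40% vs 50% | 1.34 | 1.20 | 0.89 |
| 0.20, 0.60 | 40% vs 50% | 2.11 | 1.92 | 0.91 |
| 0.10, 0.40 | 30% vs 60% | 1.49 | 1.06 | 0.71 |
| 0.20, 0.60 | 30% vs 60% | 2.30 | 1.73 | 0.75 |

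At the plan's own 10-point difference, the arms differ by n·p·0.10·(f1 − f0). This is at most 96 × 0.05 × 0.10 × 1 = 0.48 of a patient. With f1 − f0 = 0.4 it is 0.19.

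**5. Precision of an added comparison.** Half-width = 1.96·√(2p(1 − p)/n), with the same rate in both arms:

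| Assumed rate | n = 86 | n = 96 |
|---|---|---|
| 5% | ±6.5 points | ±6.2 points |
| 10% | ±9.0 | ±8.5 |
| 20% | ±12.0 | ±11.3 |

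For 5% versus 10% with n = 86, the standard error is √((0.0475 + 0.09)/86) = 0.0400. Power is Φ(0.05/0.0400 − 1.96) = 0.24. With n = 96 it is 0.26.

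**6. Why event dates are needed.** Section 2.3 states: "There will be no strict visit windows to allow for visit scheduling flexibility". Taking its couple of weeks as 14 days, the 1-month visit falls at about day 16-44 (30 ± 14) and the 3-month visit at about day 76-104 (90 ± 14). Only dated events can be counted to the same day in both arms. The chart review runs 90 days from discharge, so it always reaches day 90 from surgery.

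**The case against.** The 90-day review may already catch the events that matter most. Treatment-related is undefined. If treatment includes the operation, a serious surgical complication leading to readmission or reoperation qualifies, and the sentence setting the 90 days says only SAEs. Same-day discharges get a next-morning pain call, and patients who have not passed gas are followed by telephone, so the earliest leavers are not unobserved. The general sentence in section 2.4 on categorical comparisons would cover yes/no fields once they are added. Appendix D, the follow-up form, is not shown and may list more than Table 1. The aims are pain, opioid use, ventilation and stay, and the plan reports feasibility at 6 mmHg in over 300 patients.

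Much of this stands, and it lowers the priority. It does not close the gap. A pain call or a gas call does not record an emergency visit, and passing gas is not a diagnosis of treated ileus. Non-serious returns and those judged unrelated stay unlisted on either reading of treatment-related. Section 2.2 presents Table 1 as the data to be collected, so it is the fair basis for the reading.

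**Conclusion.** The point holds as a gap in what is listed. Aim 4 has no all-cause count of returns to care by arm from a common starting point. The conclusion rests on Table 1 as shown and on treatment-related being a real filter. If Appendix D or the SAE procedure already records all-cause returns, only the reporting part remains.

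Three stronger readings are tempting, and the documents do not support them:
- A reader might infer that harm after discharge goes unrecorded. It does not: SAEs, several week-1 items, leg weakness and telephone contacts are collected.
- A reader might infer a material bias towards 6 mmHg in wound infection and ileus. At the plan's 10-point difference and an assumed 5% risk it cannot exceed about half a patient per arm. Keeping patients with early complications in hospital would shrink it further. A shorter stay is also only something the plan says might follow.
- A reader might take the 10-point difference as the number of returns lost. It counts patients whose discharge day moves, not patients who come back.

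The pain, opioid and ventilation aims are unaffected. Priority is low to moderate.

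**What to change.** **Collection (section 2.3 and Table 1).** For every randomised patient, record readmission, emergency visit and reoperation, plus wound infection and treated ileus. Give each a date and record it whatever the judged relatedness. Count from surgery to one common day in both arms, either 30 or 90, stated in advance. Use the existing 90-day chart review and add one standard question at the 1-week, 1-month and 3-month visits. Day 30 has an advantage: even a 3-month visit at about day 76 falls after it, so patient report can cover the whole window. Define serious and treatment-related; relatedness is then needed only for IRB reporting.

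**Analysis (section 2.4).** Report these outcomes and SAEs by randomised arm with 95% confidence intervals, next to the Aim 4 results, and label them descriptive. At a 5% rate, 86 patients give only 4.3 expected events per arm, so a score-type interval for the difference is preferable to the simple formula used above.

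**Cost.** The change needs an IRB amendment, a few fields on the follow-up form and in REDCap, and a somewhat wider chart review for about 192 patients already under review. It needs no new visits and no follow-up beyond the present horizon. Returns to other hospitals will be captured only if patients report them. The intervals will be wide, so the result can inform the reading of Aim 4 but cannot establish safety.

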Since first described in 2001, robotic assisted laparoscopic prostatectomy (RALP) has been traditionally performed at a pneumoperitoneal insufflation pressure of 12-15 mmHg, derived from standard practice used during laparoscopic surgeries. Abdominal insufflation with carbon dioxide causes a multitude of known physiologic changes including increased peak airway pressures, depressed cardiac output, oliguria, and systemic acidosis, many of which show dose-dependent improvement with the reduction of intraoperative pressures.

Reducing intraperitoneal stretch with lower intra-abdominal pressures may also improve postoperative pain and facilitate earlier hospital discharge as evidenced by studies in general surgery comparing outcomes following laparoscopic cholecystectomy. Despite these results, few surgeons perform RALP at reduced pressure likely due to habit or the perceived concern for poorer visibility, compromised hemostasis, and/or technical difficulty. Furthermore, some have even proposed performing RALP at an increased pressure of 20 mmHg in an effort to achieve better hemostasis despite other physiologic consequences. There remains a paucity of data exploring the feasibility and potential benefits of performing RALP at low insufflation pressures, and no studies have explored how high the pneumoperitoneal pressure must be to perform RALP or, in other words, the minimum pressure that is adequate.

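### The one stated rule for tracking serious adverse events counts from discharge and names only chart review; it should start at incision and use the scheduled visits

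*Combined protocol and SAP*

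**What the plan says.** The safety text follows Table 3 in Section 2.3 (Study Design). It limits the scope: "we will not be tracking treatment-related AEs, only treatment-related serious adverse events (SAEs"). These are to be reported to the IRB "within 10 business days of discovery or notification of the event". The period and method of tracking come in one sentence: "SAEs will be tracked for 90 days following discharge via chart review".

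Two other parts of the plan bear on this. Section 2.2, after Table 1, says: "We will collect information on pertinent surgical outcomes that occur through discharge". Earlier in Section 2.3, visits are scheduled at about 1 week, 1 month and 3 months, and Table 3 assigns a follow-up data collection form (Appendix D) to each.

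**The concern.** The arms differ by design only in insufflation pressure, which is applied during surgery. Section 1.1 places the relevant worries there. For low pressure they are "the perceived concern for poorer visibility, compromised hemostasis, and/or technical difficulty". For insufflation in general they are airway pressure, cardiac output, urine output and acidosis. A window that opens at discharge opens after the exposure has ended. An event that is serious because it prolonged the stay also occurs before that window opens.

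The second worry is the source. A chart shows only what reaches it. Patients may be home on the day of surgery or the next day, and one who is then admitted to another hospital may not appear in the record unless somebody asks.

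The stake is the safety comparison between arms. Non-serious events are not tracked, so serious events are the main safety evidence collected under that name. Section 2.3 also says the results may encourage surgeons to use lower pressures in laparoscopic and robotic surgery generally.

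**Working it through.** The plan gives no figure to reproduce here. The check sets the passages side by side and adds a short timeline.

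**1. Start of tracking.** The tracking sentence counts from discharge. The IRB sentence sets a deadline once an event is known and gives no start date. No sentence says that tracking starts at consent, randomization or incision. The start is therefore unclear, and the only stated window, taken literally, leaves the operation and the stay uncovered.

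**2. What is recorded in hospital.** Table 1 lists blood loss, pressure increases with time and level, losses of pneumoperitoneum, device malfunctions, ventilation and hemodynamic values, free-text details of the procedure, nausea and vomiting, wound infection, hemoglobin and creatinine if drawn, length of stay, and ileus: "Clinically-significant ileus (i.e., requiring treatment; y/n"). These are data points. None records whether an event was serious or related to treatment, and transfusion, reoperation and organ injury are not defined items.

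**3. What is asked after discharge.** The follow-up items in Table 1 are the QoR-15, prescriptions, scrotal swelling and leg weakness. The phone calls on days 1 and 2 cover pain and passing gas. No item on serious events, readmission, emergency visits or outside care is listed. Section 2.2 names Epic/CareConnect and the study forms as data sources and does not describe access to outside records. Patients who miss visits stay in the analysis, and for them chart review is the only SAE source described.

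**4. Timeline in days after surgery.** Let L be the day of discharge. The stated window runs from L to L + 90.

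- L = 0: day 0 (after discharge) to day 90.
- L = 1: day 1 to day 91.
- L = 5 (an illustration, not a figure from the plan): day 5 to day 95, with days 0 to 5 uncovered on the literal reading.

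The visits fall as follows, taking a month as 365.25/12 = 30.4 days and the stated tolerance as about 14 days:

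- 1 week: day 5-7, or about day 12-14 if delayed by a week.
- 1 month: 30.4 ± 14, about day 16-44.
- 3 months: 91.3 ± 14, about day 77-105.

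For the usual discharge on day 0 or 1, the first two visits lie inside the window. The third sits at its edge and can fall on either side of the close. All three could be used to ask about events, provided that dates are recorded.

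**The case against.** The best defense is that the tracking sentence is meant to fix the end of follow-up, not its start. The IRB duty covers any treatment-related serious event that is discovered or notified, whenever it happens. This is one hospital with one surgeon, who is the PI and would be present at any intraoperative event. A major bleed with a long stay would show in blood loss, any pressure increase, any hemoglobin drawn, and length of stay, which Aim 4 compares. None of Aims 1-4 is a safety comparison.

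Much of this stands, and it rules out several stronger readings that a reader might infer:

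- *That in-hospital serious events are excluded.* The documents leave the start unstated; they do not exclude these events.
- *That Table 1 has almost no fields for in-hospital complications.* It has many, as listed above. What is uncertain is whether an event seen there is also classed and counted as serious.
- *That events treated elsewhere are lost.* The plan does not say what outside records the chart holds, and visit notes can bring such events into it. Appendix D is not in the supplied text, so an item on the form cannot be ruled out.
- *That the plan contradicts itself by also saying "There will be no extended or long-term follow-up via direct patient contact or EMR review", leaving about two weeks uncovered after an early 3-month visit.* A 90-day chart review is not evidently extended or long-term, and it does not depend on the visit date.

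The defense does not supply a start point, a process for classing in-hospital events as serious, or a described question to patients. A reporting deadline does not say who looks, when or how.

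**Conclusion.** The point holds as a gap in how ascertainment is described. The single tracking rule does not, on its wording, cover surgery or the inpatient stay. It names one source and does not use visits that are already scheduled. The literally uncovered time is typically 0-1 days, but it includes the whole exposure and lengthens with the stay. No number of missed events can be derived from the documents, and none is claimed.

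Two assumptions carry this: that the tracking sentence is applied as written, and that the unsupplied follow-up form contains no more than the items in Table 1. If either is wrong, the change merely records existing practice. The aims, the sample size and the planned tests are not affected. It is a cheap improvement, worth making so that any between-arm statement about serious events covers the period in which the arms differ.

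**What to change.** Replace the tracking sentence in Section 2.3 with:

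> Treatment-related SAEs will be tracked from initial incision through 90 days following discharge, from the operative and inpatient record, by chart review, and by asking patients at the 1-week, 1-month and 3-month visits.

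Add one item to the follow-up form (Appendix D), unless it is already there: any hospital admission, emergency department visit or procedure since the last contact, with where and when. The date is needed because the 3-month visit can fall after the window closes.

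Keep the end at 90 days after discharge. Counting 90 days from surgery instead would shorten follow-up by the length of stay: for discharge on day 5, from day 95 to day 90. The loss would be largest in the patients who stay longest.

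The cost is one sentence, one question on an existing form at existing visits, a few outside records to request, and some more SAE reports to the IRB.
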